TYPE OF STUDY

Cross sectional study. Monocentric.

INTRODUCTION

Women who wear high-heeled shoes are considered more attractive, confident and elegant. However, some authors argue that women who often use high heels are at greater risk of back pain [Lee et al 2001].

There are numerous studies that have tried to give an explanation to the typical lumbar pain in women who wear this shoe: according to some authors (Han 2015) it is due to an increase in the activity of the spinal erector (recorded by surface electromyography) which occurs both by maintaining an upright posture and by walking.

In fact, the heel produces a displacement of the center of mass (COM) anteriorly and superiorly (Gerber et al., 2012), determining compensations implemented by our body including greater activation of the paraspinal muscles (recorded by electromyography).

At a postural level, many doctors, physiotherapists and chiropractors are convinced that lower back pain induced by heels is due to an increase in lumbar lordosis associated with an anterior pelvic tilt; this thought is even shared by the American Chiropractic Association and the American Physical Therapy Association (Russell, 2010).

Furthermore, in most of the websites consulted, even by non-experts, the reason for the onset of spinal pain is attributed to hyperlordosis and pelvic anteversion.

However, this thought is not entirely in agreement with other scientific publications. Therefore it is necessary to pay attention to online searches which often answer these questions without taking EBM into account.

Investigations into the role of high-heeled shoes in altering the spinopelvic profile have attempted to explore compensatory and adaptive structural changes as the cause of lower back pain. The conclusions of these studies, however, are controversial. Some studies [de Oliveira Pezzan et al 2011; Dai et al 2015] demonstrated that high-heeled shoes significantly increase lumbar lordosis (LL), and consequently mechanical loading and degenerative changes in soft tissue.

Other studies [Franklin et al 1995] show a reduction in LL and a compensatory increase in erector spinae muscle activity [Pezzan de Oliveira et al 2011]. The results of the study of Oliveira Pezzan et al. (2011) are indicative of an increase in pelvic anteversion and LL, but only in the group of subjects who frequently wore high heels, while in the other group there was a decrease in pelvic inclination and lordosis.

The results of other studies [de Lateur et al 1991; Lee et al. 2001; Kwon et al. 2015; Schroeder and Hollander 2018] showed that heel elevation did not significantly change the LL in the female subjects evaluated.

None of the studies reported above take into consideration the time factor. In fact, all the studies have evaluated the immediate changes induced by heel raising. Women who complain of lower back pain when wearing high-heeled shoes rarely experience pain as soon as they start wearing them.

The objective of the research arises from these considerations.

The aim of this study (primary outcome) is to investigate whether wearing high-heeled shoes for at least 2 hours modifies the spinopelvic parameters compared to the barefoot condition and as soon as the shoes are worn.

The secondary outcome will be to verify in the sample analyzed whether there are different behaviors between the subgroups of those who have complained in their anamnesis and those who have never complained of lower back pain when using high-heeled shoes for a few hours.

MATERIALS AND METHODS

Location of the study

Spine Center and OSCE (Osteopathic Spine Center Education), [name]

Population

Students of the OSCE osteopathy school

Sample size

Not having found similar studies in the literature, we prefer to start as a pilot study with the recruitment of approximately 30 female subjects. This number represents a good compromise between the possibility of finding a normal distribution and the feasibility of the study.

Recruitment

Recruitment will be carried out by announcing on the bulletin board and presenting the study project in the classroom of the OSCE osteopathy school.

Following the ethical principles of the Declaration of Helsinki, a paper information will be provided where there will be an explanation of the intent and purpose of the study to all subjects before their participation; furthermore, together with the information, a paper consent will be provided on which to obtain consent written informed voluntary consent to participate in the study and consent to the use of data through privacy information.

Inclusion criteria

- female subjects aged between 20 and 40 years
- usual users of shoes with heels at least 7 cm high, with a frequency of at least twice a week and/or more than 3 hours/week as proposed by a previous study (de Oliveira Pezzan et al. 2011);

Exclusion criteria

- structural or neurological anomalies that may prevent from standing, for approximately 2 hours, with shoes having a heel (difference between the heel and the plateau) of at least 7 cm high;

Methods

A three-dimensional analysis of the posterior surface will be performed with the Formetric 4D® rasterstereographic device (Diers International GmbH, Schlangenbad, Germany). Participants will be asked to complete the informed consent form after reading the information. Furthermore, consent to the processing of data will be requested after reading the Privacy form, confirming their participation in the study.

Participants will be given a questionnaire which investigates:

- Age, weight, height of the participants;
- Any pain in the spine (measured by NPS) usually reported by subjects after using high-heeled shoes;
- Type of profession;
- Frequency with which the subjects wear the heeled shoe (how many hours per week);
- Heel height of the shoe with which they participate in the clinical study;
- Any spinal pain (measured by NPS) after wearing heeled footwear for the study period.

This last data will be filled in at the end of the evaluation.

For the evaluation of the secondary outcome, on the basis of the data from the medical history sheet, the sample will be divided into two groups:

- 1) The first group (group A, ASYMPTOMATIC) includes subjects who during daily life do not report spinal pain after wearing high-heeled shoes;
- 2) The second group (group S, SYMPTOMATIC) is made up of participants who usually complain of more or less intense pain after using the shoe.

Heel type

The subjects will be asked to bring their own pair of shoes with a heel that is at least 8.7 cm, the average height reported by the work of Schroeder and Hollander (2018), where average height means the difference between the height of the heel and the height of the raised part at the forefoot level (plateau). A particular heel width will not be required, because it seems that the height of the heel influences muscle activation, in particular the paravertebral muscles, while the width of the heel has no significant effects on them (Han 2015).

Conversely, amplitude has a greater influence on balance when standing and while walking.

Measurement method

Positioning with respect to the measurement system will be carried out according to the indications provided by the supplier.

To standardize the position the subjects will be prepared for the analysis as follows:

1. standing, back to the detection system, in a relaxed posture with knees fully extended with bare feet on the floor (neutral position)
2. bare torso with trousers and briefs lowered to mid-buttock;
3. in the case of long hair, it will be required to tie it with suitable means (cap, hair clips, hair ties, etc.) so that the neck is visible up to the hairline;
4. Rings, watches and necklaces will be removed to avoid any interference with the light lines (necklaces in particular increase this probability).

A three-dimensional analysis of the posterior surface is performed with the Formetric 4D® rasterstereographic device (Diers International GmbH, Schlangenbad, Germany) [9-15].

[figure not shown]
The device, already supplied at the Spine Center rehabilitation center in Bologna and made available free of charge for study, is non-invasive and non-dangerous. The analysis of the spine curve with rasterstereography is carried out with a purely optical modality.

The protocol

- 1) first evaluation in neutral position with bare feet (T0)
- 2) second evaluation in neutral position wearing shoes (T1);
- 3) third evaluation like the previous one but at least 2 hours apart, in which it will be required to remain standing still or walk (T2).

Parameters detected

- 1) Flexion of the antero-posterior trunk (trunk inclination – TI) measured as the angle between the vertical and the line that passes through the prominent cervical vertebra (VP) and the line that connects the two dimples (DM);
- 2) pelvic inclination angle (PI), i.e. the angle between the vertical and the tangent to the lumbosacral junction (ILS);
- 3) ITL-ILS lordotic angle, measured between the tangents of the thoracolumbar junction (ITL) and the lumbosacral junction (ILS);
- 4) ICT-ITL kyphotic angle, measured between the tangents of the cervicothoracic junction (ICT) and the thoracolumbar junction (ITL);
- 5) lumbar arrow (FL) (horizontal distance in millimeters of the lumbar spine from the virtual vertical line that passes through the kyphotic apex) ;
- 6) cervical arrow (FC) (horizontal distance in millimeters of the cervical spine from the virtual vertical line that passes through the kyphotic apex).

Statistic analysis

A descriptive analysis of the population will be performed to determine the mean values and standard deviations (SD) of both the combined group and the subgroups A and S. T-tests for independent data will be used to verify whether there are any significant differences between the two subgroups .

The distribution of the data will be verified using graphical representation. If the distribution is normal ($p <0.05$) for the comparison between T1 vs T2 the t-test for paired data will be used and between the subgroups (T1S vs T1A and T2S vs T2A) t-test for independent data with statistical significance accepted for p values <0.05 . ANOVA will be used to simultaneously compare the pre and post of both groups.

If the data does not have a normal distribution ($p >0.05$) the Wilcoxon test will be used for the comparison between the T1 vs T2 data of the total group and the Mann-Whitney U test for the comparison between subgroups (T1S vs T1A and T2S vs T2A). The Friedman test will be used to simultaneously compare the pre and post of both groups.

Risks

The risks are quite limited given that the shoes worn are those owned by the tested subject, therefore it is assumed that they are used to wearing them, and they are not asked to perform movements at risk of sprains or falls.

Benefits

Being able to identify the spino-pelvic parameters that predispose to spinal symptoms, when wearing high heels, could help prevent the related pathology/symptoms through postural re-education or muscle strengthening exercises.

Costs

The use of the Formetric will be given free of charge and any related expenses (paper, color cartridges, etc.) will be borne by the Spine Center.

References

de Lateur BJ, Giacconi RM, Questad K, Ko M, Lehmann JF. 1991. Footwear and posture: compensatory strategies for heel height. *Am J Phys Med Rehabil* 70:246–254

de Oliveira Pezzan PA, Joa˜o SMA, Ribeiro AP, Manfio EF. 2011. Postural assessment of lumbar lordosis and pelvic alignment angles in adolescent users and nonusers of high-heeled shoes. *J Manip Physiol Ther* 34:614–621

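### The symptomatic versus asymptomatic comparisons at T1 and T2 make no allowance for heel height, which is recorded, not standardised, and could differ between the groups

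*Combined protocol and SAP*

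**What the plan says.** - **Exposure.** Under Heel type, women bring their own shoes. The minimum is 8.7 cm, taken as heel height less forefoot (plateau) height. No maximum or standard height is set.
- **Recording.** The questionnaire under Methods includes "Heel height of the shoe with which they participate in the clinical study". The item does not say whether the height is measured by staff or reported by the woman, or whether it is net of the plateau.
- **Stated role of height.** Heel type leaves heel width free because "it seems that the height of the heel influences muscle activation, in particular the paravertebral muscles", whereas width does not.
- **Groups.** For the secondary outcome, "on the basis of the data from the medical history sheet, the sample will be divided into two groups": A without and S with usual pain after wearing heels. No matching or stratification is described.
- **Tests.** Under Statistic analysis, normal data are compared "between the subgroups (T1S vs T1A and T2S vs T2A) t-test for independent data". For non-normal data the plan uses "the Mann-Whitney U test for the comparison between subgroups (T1S vs T1A and T2S vs T2A"). It adds that "ANOVA will be used to simultaneously compare the pre and post of both groups", with the Friedman test as the non-normal counterpart. No covariate is named anywhere.
- **Size.** Under Sample size, "we prefer to start as a pilot study with the recruitment of approximately 30 female subjects".

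**The concern.** The secondary aim is to learn whether women with a history of pain in heels behave differently in heels from women without one. For that, S and A should face a comparable exposure, or the analysis should allow for the difference. The design does neither. Shoe height is the woman's own choice above a floor, and pain history may influence that choice. Women with pain could favour lower heels, or could have pain because they wear higher ones, so the direction of any imbalance is unknown.

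A raw difference at T1 or T2 could then come from the shoes. The Benefits section hopes to identify parameters that predispose to symptoms and to build preventive exercise on them, so a difference produced by shoe choice would be misread. The variable needed to guard against this is already on the questionnaire.

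**Working it through.** **Plan's own figure.** The sample size of about 30 rests on feasibility and the chance of a normal distribution. No effect size, SD or power is given, so there is nothing to reproduce.

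**Inputs from the documents.** About 30 women in total; significance at p < 0.05 (taken as two-sided, since sidedness is not stated); independent t-test at T1 and T2.

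**Assumed inputs, because the documents give none.** Groups of 15 and 15; within-group correlation r between heel height and the parameter, 0 to 0.5; S minus A gap in mean heel height D, 0 to 1 within-group SD; no true group difference once heel height is held fixed.

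**Step 1: spurious difference.** In outcome SDs, bias = r × D. At the largest values, 0.5 × 1 = 0.50 SD.

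**Step 2: standard error of the raw difference.** √(1/15 + 1/15) = √0.1333 = 0.365 SD.

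**Step 3: false-positive rate.** With b = (r × D)/0.365, the normal approximation is P(Z > 1.96 − b) + P(Z < −1.96 − b). For r = 0.5 and D = 1, b = 0.50/0.365 = 1.37. The upper tail is P(Z > 0.59), about 0.277, and the lower tail is below 0.001, giving 0.278.

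**Step 4: check by simulation.** 20,000 runs per row compared the unadjusted t-test with a linear model on group and heel height.

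| r | D | Bias (SD) | Unadjusted, normal approx. | Unadjusted, simulated | Adjusted, simulated |
|---|---|---|---|---|---|
| 0.2 | 0.5 | 0.10 | 5.9% | 5.6% | 4.8% |
| 0.2 | 1.0 | 0.20 | 8.5% | 8.5% | 4.9% |
| 0.3 | 0.5 | 0.15 | 7.0% | 6.8% | 5.1% |
| 0.3 | 1.0 | 0.30 | 13.0% | 12.6% | 5.2% |
| 0.5 | 0.5 | 0.25 | 10.5% | 10.4% | 5.1% |
| 0.5 | 1.0 | 0.50 | 27.8% | 27.1% | 4.9% |

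With r = 0 or D = 0, both analyses stay at about 5%. For scale, 15 versus 15 has 80% power only for a true difference of about 1.06 SD (1.12 SD if the split is 20 and 10).

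**Step 5: price of adjusting.** Residual degrees of freedom fall from 30 − 2 = 28 to 30 − 3 = 27. The variance factor of the group difference rises from 2/15 to about 2/15 + D²/28, with D the observed gap. For D = 0.5 this is 0.1333 + 0.0089 = 0.1423, so the standard error is √(0.1423/0.1333) = 1.03 times as large. For D = 1 it is 0.1333 + 0.0357 = 0.1690, a ratio of 1.13. Against this, residual variance falls by the factor 1 − r². At r = 0.5 and D = 1 the two roughly cancel: 0.75 × 0.1690 = 0.127, against 0.1333.

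**Step 6: inaccurate heights.** If recorded height has reliability λ within groups and its errors are unrelated to group, the fitted slope shrinks by λ, and a bias of about r × D × (1 − λ) remains. The return to 5% in the table is therefore a best case.

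**Step 7: does the planned ANOVA close the gap?** The plan does not define pre and post. If the analysis is a group-by-time ANOVA, its interaction compares within-woman changes, and stable barefoot differences cancel. If pre is T1 and post is T2, a heel effect that is constant over the two hours cancels too. If pre is T0, when no shoe is worn, the heel effect stays in the change. On either reading, the separate tests at T1 and at T2 remain unadjusted.

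**The case against.** The strongest reply is that heel height is only a possible confounder. The remark under Heel type is tentative, concerns muscle activation, and serves to justify not specifying heel width. Muscle activation is not an outcome; the six parameters are angles and distances of the back surface. The Introduction calls the evidence on posture controversial and cites studies with no significant change in lordosis. Nothing in the documents quantifies a gradient among women who all wear at least 8.7 cm. All of this stands. A reader might infer that the protocol itself says heel height drives the outcomes, or that S and A will wear different heels; the documents support neither. What survives is that an imbalance cannot be ruled out before data collection, so the allowance has to be specified in advance. The planned subgroup descriptives might reveal an imbalance but would not adjust for it.

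A second reply is that this is a secondary aim of a pilot. That limits the weight of the point, but the tests are still to be read at p < 0.05.

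A reader might also infer that the main T1 versus T2 result is compromised. It is not: that comparison is within each woman, and T2 repeats the T1 set-up, apparently in the same shoe.

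Finally, one might want to require adjustment for the barefoot value. If T0 correlates 0.6 to 0.8 with the later value (assumed), it would remove 36% to 64% of the residual variance. But S and A are not randomised, so T0-adjusted and change-score analyses can disagree (Lord's paradox), and barefoot posture may be part of what predisposes to symptoms. The documents do not settle which estimate is wanted.

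**Conclusion.** The point holds for the secondary S versus A comparisons at T1 and T2 only. They ignore a recorded exposure variable that the design leaves free to differ between self-formed groups. Under the assumed ranges the false-positive rate runs from about 5%, when either the correlation or the heel gap is zero, to about 27% when both are at their upper end. Adjustment returns it to about 5%, less fully if recorded heights are inaccurate. The range is wholly conditional: group sizes, heel-height spread, heel gap and correlation are all absent from the documents. The planned ANOVA names no covariate and removes a constant heel effect only if pre means T1. Given the pilot setting and the secondary aim, this is a worthwhile, low-cost improvement and not a defect that undermines the study.

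**What to change.** 1. Report the heel height of the study shoe by group, with mean and SD.
2. For each parameter, estimate the S versus A difference at T1 and at T2 from a linear model with group and heel height, and give it with a 95% CI. Use this model in place of the independent t-test. If the data are judged non-normal, report it beside the Mann-Whitney result.
3. Word the questionnaire item so that the recorded height is heel minus plateau, matching the definition under Heel type.
4. Present a model that also includes T0 as a supporting analysis, not as the required one. Add no further covariates at this sample size.
5. State which time points pre and post denote in the ANOVA.

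**Cost.** Changes to the statistical section and to one questionnaire item; no additional variable is collected. The main model spends one residual degree of freedom, and the supporting model two (30 − 4 = 26 left). Some precision is lost if heel height differs between the groups: the standard error grows by about 3% at a 0.5 SD gap and 13% at a 1 SD gap, before any gain from lower residual variance. The model assumes a linear heel effect with the same slope in both groups.

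### Does asking for a study shoe of at least 8.7 cm, when eligibility is set at 7 cm, undermine the assumption that women are used to the shoe?

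*Combined protocol and SAP*

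**What the plan says.** Heel height appears in three rules of the combined protocol and SAP.

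- **Inclusion criteria:** participants are "usual users of shoes with heels at least 7 cm high", with a minimum weekly frequency or duration of use. Whether the plateau is subtracted is not stated.
- **Exclusion criteria:** women are excluded if a structural or neurological problem could stop them standing for about 2 hours "with shoes having a heel (difference between the heel and the plateau) of at least 7 cm high".
- **Heel type:** "The subjects will be asked to bring their own pair of shoes with a heel that is at least 8.7 cm". The figure is attributed to a cited study, "where average height means the difference between the height of the heel and the height of the raised part at the forefoot level (plateau").

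The questionnaire topics under Methods include "Heel height of the shoe with which they participate in the clinical study" and "Frequency with which the subjects wear the heeled shoe (how many hours per week"). They also include spinal pain usually felt after wearing heels, and spinal pain after the study period. Usual heel height is not listed. The Risks section infers from ownership that women are used to the shoes, and adds that nobody is asked to make movements that risk a sprain or fall.

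**The concern.** The height that qualifies a woman as a habitual wearer is lower than the height of the shoe she is asked to wear for 2 hours or more. Someone who usually wears 7.5 cm heels and owns a rarely used 9 cm pair satisfies every written rule, although nothing shows that she is used to the 9 cm pair. Three things could be at stake.

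1. **Risk statement.** Part of the case for low risk is familiarity with the shoe, and no criterion secures that at 8.7 cm.
2. **Habituation.** The Introduction cites a study in which pelvic anteversion and lordosis increased, "but only in the group of subjects who frequently wore high heels, while in the other group there was a decrease in pelvic inclination" (lordosis fell there too). By the plan's own background, then, habituation may alter the response being measured.
3. **Group labels.** Group A comprises "subjects who during daily life do not report spinal pain after wearing high-heeled shoes", with no height given. For some women the label could describe a lower heel than the one tested.

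The listed questionnaire topics would not let the team count such women.

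**Working it through.** The plan gives no figure to reproduce on this point. The sample of approximately 30 is a pilot choice made on feasibility and distributional grounds, with no power calculation. The check compares the thresholds and then follows the difference into the planned comparisons.

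**Size of the gap**

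- Inputs: 7 cm (Inclusion criteria; Exclusion criteria) and 8.7 cm (Heel type).
- Difference between the minimums: 8.7 − 7.0 = 1.7 cm.
- Relative size: 8.7 / 7.0 = 1.243, so the study-shoe minimum is about 24% higher; 7.0 / 8.7 = 0.805, so the eligibility minimum is about 80% of it.
- If the inclusion height were gross, with a plateau of p cm, the gap would be 8.7 − (7.0 − p) = 1.7 + p. The document does not give p. Assuming 0 to 2 cm, the range is 1.7 to 3.7 cm. Both places that define height use heel minus plateau, so the net reading is the natural one and 1.7 cm the working figure.
- The 1.7 cm separates two minimums. It does not cap the step for any one woman, because Heel type sets no upper limit.

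**Are the rules compatible?** Yes. A shoe of 8.7 cm or more is also a shoe of 7 cm or more. One height defines who counts as a wearer, one defines who can physically stand in heels, and one describes the shoe requested on the day.

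**Effect on the planned comparisons**

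| Comparison | Role of heel height |
|---|---|
| T1 vs T2 | Each woman is her own control, and the third evaluation repeats the second after at least 2 hours. Height differences between women cannot confound it. |
| Barefoot (T0) vs shod, named in the aim | Also within-woman. Height affects which shoe the average describes, and that height is recorded. |
| Group A vs group S | Could be affected only if the groups differ in how far the test shoe exceeds the usual one. Nothing in the document indicates that they do. |

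**Would equal thresholds secure familiarity?** Not fully. With one minimum throughout, a woman could still bring a pair taller than her usual one. Aligning the figures would tidy the text without establishing that each woman is used to the pair she brings.

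**The case for a change.** The strongest case for acting is that usual heel height is cheap to ask and hard to recover later. One extra questionnaire item would show how many women were tested above their usual height, overall and in groups A and S. One sentence would say what happens to an eligible woman who has no shoe of the requested height. The plan itself treats habituation as relevant, since it makes habitual use an entry criterion.

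Part of this stands. The text does not say why the heights differ, does not cover the woman without such a shoe, and leaves unclear which shoe the hours-per-week topic means. Familiarity at 8.7 cm does rest on ownership rather than on a criterion.

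The rest carries less weight:

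- The cited study contrasts frequent wearers with others, and this plan already restricts entry to frequent wearers. It does not show that a step of 1.7 cm turns a habitual wearer into an unaccustomed one.
- Risks states familiarity openly as an assumption, and gives the absence of hazardous movements as a second ground.
- Pain after the study period is recorded, so a mismatch between the group label and pain in the tested shoe can be seen.
- The questionnaire is described only by topic, so ambiguity in a topic heading is weak evidence of ambiguity on the form.

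**Conclusion.** The difference is real, at 1.7 cm between the two minimums, but it is a gap in explanation and not a flaw in the design. The rules do not conflict, and the source of the 8.7 cm figure is given. The within-woman comparisons are not confounded by heel height. No bias between groups A and S is shown, no loss of precision can be derived, and no planned test would differ. Between none and all of the approximately 30 women could be affected; the document does not allow a narrower range.

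This rests on two assumptions: that the inclusion height is net of plateau, as in the two places where height is defined, and that each woman wears the same pair at T1 and T2, as the description of the third evaluation implies. If the first fails, the gap widens by the unknown plateau height, but the reasoning on the comparisons is unaffected.

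The investigators may wish to use one definition of height across the inclusion, exclusion, Heel type and Risks text, say how a woman without such a shoe is handled, and note usual heel height descriptively. These are optional clarifications. No view is taken here on which height is right.

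### Heel wear before the barefoot scan is neither restricted nor recorded, so T0 and T1 may not be the unexposed and just-put-on references the primary aim needs

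*Combined protocol and SAP*

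**What the plan says.** The primary aim, at the end of the Introduction, takes two hours or more in heels as the condition of interest and names its references as "compared to the barefoot condition and as soon as the shoes are worn". The paragraphs before it argue that earlier studies looked only at immediate changes and left out time, so duration of wear is the exposure under study.

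The Inclusion criteria admit habitual wearers of heels of 7 cm or more, "with a frequency of at least twice a week and/or more than 3 hours/week". The single exclusion criterion concerns "structural or neurological anomalies that may prevent from standing, for approximately 2 hours"; it says nothing about recent wear.

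On footwear before the visit, the Heel type section says only: "The subjects will be asked to bring their own pair of shoes with a heel that is at least 8.7 cm". The preparation list under Measurement method covers posture, bare feet, clothing, hair and jewellery. The protocol section then goes straight to the barefoot T0, the shod T1, and T2 at least two hours later.

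The one questionnaire item on how much heels are worn is "Frequency with which the subjects wear the heeled shoe (how many hours per week", which is a usual weekly amount. The Statistic analysis section tests T1 against T2 in the whole group with a paired t-test or Wilcoxon test.

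**The concern.** If duration in heels is the exposure, prior duration should be near zero at T0 and T1. The plan does not secure this. A woman who wore heels for some hours, took them off for T0 and put a pair back on for T1 has followed every instruction. Her T0 may then not be an unexposed reference, and her T1 may already contain part of the change that T2 is meant to show.

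What is at stake is the whole-group T1 versus T2 comparison. Under some plausible time courses it would be pulled towards finding no effect of time, which is the very question asked. Because same-day wear is not recorded, the affected women could not be identified afterwards, and no sensitivity analysis could be run.

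**Working it through.** **1. What is controlled and what is not**

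| Needed by the aim | What the plan provides |
|---|---|
| Barefoot reference without recent heel exposure | Bare feet at T0; no heel-free interval, rest period or arrival-footwear rule |
| Shod reference with no accumulated wear | The aim describes it as just put on, and T1 follows T0; earlier wear that day is unrestricted |
| Means of identifying pre-exposed women | Usual hours per week only |

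**2. When prior wear biases the contrasts**

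Let B be a woman's unexposed barefoot value, I the immediate effect of putting the shoes on, and D the added effect of two hours' wear.

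- *No carry-over:* T1 = B + I and T2 = B + I + D, so T2 − T1 = D. No bias.
- *Residual r that simply adds, effect linear in time:* T1 = B + I + r and T2 = B + I + r + D, so T2 − T1 = D. The residual cancels within the woman.
- *Effect that persists and levels off, with a share a of D already present at T1:* T1 = B + I + aD and T2 = B + I + D, so T2 − T1 = (1 − a)D. If a fraction f of women are pre-exposed, the mean change is D(1 − f × a).
- *Effect that accelerates with time:* T2 − T1 exceeds D.

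For T2 − T0 in the levelling-off case, suppose the residual aD is also present barefoot. A pre-exposed woman then shows I + (1 − a)D. The proportional loss in the mean is f × a × D / (I + D), not f × a. If I and D have opposite signs, the contrast can become larger in size. The Introduction cites lordosis changes in both directions, so the signs cannot be taken as known.

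**3. How often could it happen?**

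The frequency criterion reads "with a frequency of at least twice a week and/or more than 3 hours/week". The and/or admits one weekly session of more than 3 hours, so the eligibility floor is one or two wearing days a week: 1/7 = 0.14 or 2/7 = 0.29. Neither is an estimate of f. Evening wear counts in these fractions but does not matter for an earlier scan, and behaviour on the test day is unknown.

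**4. Illustration for T2 − T1, levelling-off case only**

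The plan's sample size of about 30 has no effect size, SD or power behind it, so there is no figure to reproduce. As a yardstick, take n = 30, a paired t-test (noncentral t) and alpha 0.05, two-sided by assumption because the plan does not say. Power is 80% at a standardised change d = 0.529.

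With pre-exposure, the mean becomes d(1 − f × a) and the variance 1 + (a × d)² × f(1 − f). For f = 2/7 and a = 0.5:

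- mean = 0.529 × (1 − 0.143) = 0.454
- variance = 1 + 0.0700 × 0.2041 = 1.014
- effective d = 0.454 / √1.014 = 0.450, giving power of 66.5%

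| f (assumed) | a (assumed) | Shrinkage f × a | Power |
|---|---|---|---|
| any | 0 | 0% | 80% |
| 1/7 | 0.5 | 7% | 73.6% |
| 1/7 | 1 | 14% | 65.6% |
| 2/7 | 0.5 | 14% | 66.5% |
| 2/7 | 1 | 29% | 49.5% |
| 0.5 | 0.5 | 25% | 54.9% |
| 0.5 | 1 | 50% | 27.3% |

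The last two rows show sensitivity only; nothing in the documents supports f = 0.5. The value a = 1 would require the full two-hour change to survive shoe removal, preparation and the T0 scan.

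**The case against.** The strongest reply is that each woman is her own control, so a residual present at both T1 and T2 cancels. Attenuation needs the further assumption that the effect levels off, and the documents give no time course. This stands: the direction of any bias is not established.

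Second, asking women to bring shoes most naturally means carrying them. The study pair must be at least 8.7 cm while eligibility needs only 7 cm, so it need not be the everyday pair. This makes prior wear of that pair less likely. It does not bar wearing that pair, or other heels, beforehand.

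Third, the aim already describes the T1 reference as "compared to the barefoot condition and as soon as the shoes are worn", and T1 follows the barefoot scan. This stands as regards the delay between putting the shoes on and T1. It does not deal with wear before T0.

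A reader might also infer that women with and without heel pain differ in same-day wear, so that the S versus A comparisons are biased. No section supports that; it is a possibility only. Long-term adaptation is not the issue either, since habitual users are the intended population.

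Finally, this is a self-described pilot. That lowers the stakes, but a pilot is also where the measurement procedure should be settled.

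**Conclusion.** The gap is real: the exposure under study is neither restricted nor recorded before the reference scans, in a population selected for that exposure. T0 and T1 may therefore fail to be the unexposed and just-put-on references.

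A reader might go further and conclude that the references are invalid, that the result must be biased towards no effect, or that at least 29% of women will arrive pre-exposed. The documents support none of these. Attenuation of T2 − T1 requires that some women arrive pre-exposed, that an effect persists through T0, and that it levels off. If carry-over is nil or additive, T2 − T1 is unbiased. The eligibility floor is 1/7 to 2/7 wearing days, which is not the share exposed before a scan. The percentages under the working rest on assumed f and a, start at 0, and apply to T2 − T1 only.

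The case for acting rests on the low cost of the fix and on the loss being unrecoverable once scans are done, not on a demonstrated bias.

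**What to change.** In The protocol, before T0, add: *Participants arrive in flat shoes, carrying the study heels, and have not worn heels that day before T0. A participant who has worn heels that day is re-booked.* The investigators may substitute another heel-free interval if they justify it; the documents do not allow a length to be derived.

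In the questionnaire under Methods, add an item for the date and hours of last heel wear. This allows a sensitivity analysis of T1 versus T2 by recent wear.

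The cost is one line in the participant instructions, one questionnaire item and an occasional re-booked session. Both changes need to be in place before the first scan.
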